6.3.4 Factor analysis, impact of symptoms e-diary items

Exploratory factor analysis will be undertaken in an attempt to study the underlying concepts of the impact e-diary items, using the mean score during the last seven registrations prior to visit 2 for the items that are reported on an 11-graded scale. If two or more registrations are missing during the seven day period for a patient, the mean value will be set to missing. Principal components factor analyses with varimax and oblimin rotation will be used. All loadings for the retained factors will be presented.

6.3.5 Reliability

6.3.5.1 Test retest, modified QOLRAD

Test-retest reliability will be investigated for the modified QOLRAD using Intraclass Correlation Coefficients (ICC). The within-patient and between-patient mean square will be calculated by two-way analysis of variance (ANOVA) with the factors of patient and visit (1 and 2), using subjects in a stable condition between visit 1 and 2. A stable patients is defined as a patient who had “About the same”, “Almost the same, hardly worse at all” or “Almost the same, hardly better at all” on OTE at visit 2. The ICC will be calculated for the derived clusters of the modified QOLRAD obtained through the factor analysis described in section 6.3.3. A cluster score will be calculated as the mean value of the items in the cluster. Other ways of calculating cluster scores may be explored. The test-retest reliability intraclass correlation coefficient (R) will be estimated as:

$$\hat{R} = \frac{BMS - WMS}{BMS + (k_0 - 1)WMS}$$

where BMS and WMS are the mean square values between-patients and within-patients respectively, and k_0 denotes the number of replicates per patient (two in this case).

A 95% confidence interval for R will be estimated as

$$R \geq \frac{\frac{BMS}{WMS} - F_{N-1, K-N, \alpha/2}}{\frac{BMS}{WMS} + (2-1)F_{N-1, K-N, \alpha/2}}, \quad R \leq \frac{\frac{BMS}{WMS} - F_{N-1, K-N, 1-\alpha/2}}{\frac{BMS}{WMS} + (2-1)F_{N-1, K-N, 1-\alpha/2}}$$

where N = number of patients and K = number of measurements.

In order to be included in the test-retest calculations, a patient has to have non-missing cluster scores at both visit 1 and visit 2.

ICC values < 0.4 will be considered to represent poor reliability, values > 0.75 excellent reliability, and values in between fair to good reliability (Fleiss 1986).

Missing values

If a patient answered less than 50% of the items in a cluster, the cluster score will be set to missing.

6.3.5.2 Internal consistency

The consistency of questions within the modified RDQ symptom clusters and modified QOLRAD clusters will be evaluated using Cronbach's alpha coefficient (Cronbach 1951). Cronbach's alpha will be estimated as

$$\alpha_c = \frac{m}{m-1} \left(1 - \frac{\sum Var(x_i)}{Var(\sum x_i)} \right)$$

where m is the number of items in the cluster, $Var(x_i)$ is the estimated variance of the i^{th} item and the summation is over all items within a cluster. Ninety five% confidence intervals for Cronbach's alpha coefficients will be presented. A high alpha coefficient suggests that the items within a cluster measure the same construct. A minimum value of 0.70 has been recommended (Fayers et al 2007).

For the modified RDQ, Cronbach's alpha will be calculated for each multi-item symptom cluster derived through the factor analysis of 24 h period values (see section 6.3.2. Item scores will be defined as the mean or maximum intensity (see section 6.3.1 of the last 7 days prior to visit 2.

For the modified QOLRAD, Cronbach's alpha will be calculated for each multi-item cluster derived through the factor analysis described in section 6.3.3, using the item responses at visit 2.

6.3.6 Construct validity

6.3.6.1 Convergent and discriminant validity

The correlation between symptom clusters in the modified RDQ and modified QOLRAD and dimensions in other instruments will be investigated using Spearman's rho. 'Convergent' refers to the idea that high correlations are expected between those dimensions that are theoretically related and 'discriminant' to the idea that low correlations are expected between those dimensions that are theoretically unrelated.

For the modified RDQ, symptom clusters derived through the factor analysis of 24 h period values (see section 6.3.2) will be used. Symptom cluster scores will be defined as the mean or maximum (see section 6.3.1) daily symptom cluster intensity of the last 7 days prior to visit 2.

For the modified QOLRAD, the derived clusters as described in section 6.3.3 will be used. The responses (visit 1 or visit 2) used will vary depending on the availability of the reference instruments (see below).

The following instruments will be used to evaluate convergent and discriminant validity of the modified RDQ and modified QOLRAD:

- Modified RDQ vs GSRS: GSRS dimension scores will be based on responses at visit 2.
- Modified QOLRAD vs GSRS: Modified QOLRAD and GSRS dimension scores will be based on responses at visit 1 as well as visit 2.
- Modified QOLRAD vs SF-36v2 acute: Modified QOLRAD and SF-36v2 acute dimension scores will be based on responses at visit 2. The eight SF-36v2 acute dimensions and two summary dimensions described in section 4.2.4.1 will be used.
- Modified QOLRAD vs MOS sleep scale: Modified QOLRAD and MOS sleep scale dimension scores will be based on responses at visit 1 as well as visit 2.
- Modified QOLRAD vs HADS: Modified QOLRAD and HADS dimension scores will be based on responses at visit 1.

The correlation coefficients (Spearman's rho) will be presented.

Missing values

If a patient answered less than 50% of the items in a dimension, the dimension score will be set to missing.

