2. STUDY OBJECTIVES

2.1 Objectives related to validation

- To determine which symptoms in the modified RDQ e-diary are relevant for the target patient population
- To establish the validity, reliability, and ability to detect change (responsiveness) of the modified RDQ e-diary in the target patient population
- To establish the clinically meaningful change of the modified RDQ e-diary in the target patient population
- To determine which symptoms or symptom domains from the modified RDQ e-diary will form the basis for the primary endpoint in future studies in the target patient population
- To determine a responder definition in the target patient population
- To investigate the validity, reliability and ability to detect change (responsiveness) of the modified QOLRAD for assessing the impact of GERD symptoms in the target patient population
- To investigate the validity of alternative diary based PRO instruments for assessing the impact of GERD symptoms in the target patient population

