4.2 Patient-Reported Outcomes (PROs)

The measurement approach of PROs will focus on establishing the validity, reliability, and ability to detect change (responsiveness) and establish clinically meaningful change of the modified RDQ e-diary in the target patient population. In addition, a responder definition will be established. The validity and reliability of a disease specific measure of the impact of GERD symptoms (modified QOLRAD) in the target patient population will also be assessed.

Several PRO instruments will be used as references when establishing the validity, reliability, and ability to detect change (responsiveness) and clinically meaningful change of the modified RDQ e-diary (GSRS, section 4.2.3, SF-36 v2 acute, section 4.2.4, modified QOLRAD, section 4.2.5, OTE, section 4.2.9). When establishing the responder definition of the modified RDQ e-diary, the TSQ-G, section 4.2.8, and sufficient symptom control question, section 4.2.10, will be used as references. When determining which symptoms in the modified RDQ e-diary are most relevant for the target patient population, the “Most troublesome symptoms” items, section 4.2.2, will be used as a reference.

To determine the validity and reliability of the modified QOLRAD the following instruments will be used: GSRS, section 4.2.3, SF-36 v2 acute, section 4.2.4, the MOS Sleep Scale, section 4.2.7, OTE, section 4.2.9, HADS, section 4.2.11.

HADS, section 4.2.11 will also be used for descriptive purposes.

All PRO instruments will be completed by patients using hand-held electronic devices (see section 4.2.13).

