4.2.6 Impact of Symptoms e-diary items

In order to evaluate alternative diary based PRO instruments for the assessment of the impact of GERD symptoms in the target patient population, the e-diary will include a set of "Impact of Symptoms e-diary items".

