6.3.6.2 Known groups validity

The GSRS reflux syndrome dimension scores (see section 4.2.3) from visit 2 will be used to separate patients into three groups that can be expected to score differently in questions regarding heartburn and acid regurgitation in other instruments. The cut-off for the separation

will be based on previous data. The mean cluster score of the modified RDQ symptom clusters and modified QOLRAD clusters will be presented graphically by GSRS group.

For the modified RDQ, the derived symptom clusters of 24 h period values (see section 6.3.2) will be used. Symptom cluster scores will be defined as the mean or maximum (see section 6.3.1) daily symptom cluster intensity of the last 7 days prior to visit 2.

For the modified QOLRAD, the derived clusters (see section 6.3.3) will be used, using responses at visit 2.

Missing values

If a patient answered less than 50% of the items in a cluster, the cluster score will be set to missing.

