6.3.7.6 Impact of symptoms e-diary items

For the items with responses on an 11 point NRS and the derived clusters (see section 6.3.4), the mean value will be presented graphically by day for the last seven days prior to visit 2. A cluster score will be calculated as the mean value of the item responses in the cluster.

Descriptive statistics will be calculated for the morning report items

- How long did it take you to fall asleep last night?
- How many times did you wake up after falling asleep?
- After falling asleep for the first time, how much total time did you spend awake during the night?
- How long did you sleep last night?

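### The protocol sets out to investigate the validity of the Impact of Symptoms e-diary items but plans no convergent, discriminant or known-groups analysis for them

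*Protocol*

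**What the plan says.** Protocol 2.1 lists seven validation objectives. The last is "To investigate the validity of alternative diary based PRO instruments for assessing the impact of GERD symptoms in the target patient population". Section 4.2.6 provides the Impact of Symptoms e-diary items for this purpose. Section 4.2.6.1 says they cover the areas of daily impact reflected in the QOLRAD and are completed morning and evening from visit 1 to visit 5.

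In the Part 1 analyses the items appear in two places:

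- 6.3.4: "Exploratory factor analysis will be undertaken in an attempt to study the underlying concepts of the impact e-diary items", using the mean of the last seven registrations before visit 2 for items on the 11-point scale.
- 6.3.7.6: for those items and the derived clusters, "the mean value will be presented graphically by day for the last seven days prior to visit 2". Four sleep time and count items get descriptive statistics.

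Construct validity is section 6.3.6, which has two parts. The first, 6.3.6.1, is introduced by "The following instruments will be used to evaluate convergent and discriminant validity of the modified RDQ and modified QOLRAD". The second, 6.3.6.2, divides patients into three groups by the GSRS reflux dimension at visit 2 and states: "The mean cluster score of the modified RDQ symptom clusters and modified QOLRAD clusters will be presented graphically by GSRS group".

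Section 6.1 announces a SAP for analyses that involve Part 2, that is post-randomisation, data.

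**The concern.** Factor analysis shows which items group together. Plots by day show their level and how it moves. Neither shows whether the diary items measure the impact they are meant to measure. The protocol's own tools for that question are correlation with related and unrelated scales and comparison across known groups. It applies both to the modified RDQ and the modified QOLRAD, and neither to the impact diary.

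At stake is whether Part 1 can say anything about the diary items as an alternative to a recall questionnaire such as the modified QOLRAD. Patients answer 12 morning and 23 bedtime impact items (Appendix I) every day until visit 5, so a good deal of patient effort goes into this objective.

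**Working it through.** No alpha, power or sample-size figure bears on this point. The check traces the instrument from its objective to the analyses.

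**1. Analyses of the impact items in 6.3**

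| Section | Analysis | Impact items included? |
|---|---|---|
| 6.3.4 | Exploratory factor analysis | Yes |
| 6.3.6.1 | Convergent and discriminant correlations | No |
| 6.3.6.2 | Known groups by GSRS reflux dimension | No |
| 6.3.7.6 | Daily means, descriptive statistics | Yes |

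**2. The pairings in 6.3.6.1**

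- Modified RDQ with GSRS (one).
- Modified QOLRAD with GSRS, SF-36v2 acute, MOS Sleep and HADS (four).

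That is 1 + 4 = 5 pairings, of which 0 contain the impact items.

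**3. Could another part of the protocol fill the gap?**

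- Section 6.5 (Part 2) covers test-retest of the modified RDQ, effect sizes by OTE class and clinically meaningful change. Effect sizes address responsiveness, not construct validity.
- The cognitive interviews (4.3.1) ask whether impact concepts are relevant to patients. That is content validity at the level of concepts, in about 40 patients, and is reported separately from the clinical study report.
- The SAP is announced for Part 2 data (6.1). The Part 1 analyses are the ones written in 6.3.

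**4. Are suitable comparators available?**

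Table 3 has modified QOLRAD, MOS Sleep, SF-36v2 acute and GSRS all completed at visit 2. Each refers to the past week: 4.2.4.1 for SF-36v2 acute, 4.2.7.1 for MOS Sleep as used here, and Appendices F and H for GSRS and QOLRAD. The diary score in 6.3.4 uses the last seven registrations before visit 2, so the periods largely coincide. A cluster score (mean of the items, 6.3.7.6) and a missing-data rule (two or more registrations missing, 6.3.4) are already defined.

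**5. Items outside the clusters**

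All 23 bedtime items and 3 of the 12 morning items are on the 11-point scale, so 26 can enter the clusters. The other 12 - 3 = 9 morning items cannot. Four of these are the time and count items in 6.3.7.6; the other five are yes/no or clock-time entries. Cluster correlations alone would therefore leave the time and count items untested.

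**6. Precision of the added correlations (illustration)**

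Assume r = 0.5 and n = 450. Fisher z is 0.549, with half-width 1.96/sqrt(447) = 0.093. The limits 0.456 and 0.642 transform back to about 0.43 and 0.57. The interval for Spearman's rho is slightly wider. About 500 patients are planned for Part 1, so n may be larger. This shows only that the added analyses would be informative; it does not measure the size of the gap.

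**The case against.** The strongest reply has three parts.

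First, the objective says investigate, whereas the modified RDQ objective says establish. Factor analysis is evidence on structure, and the interviews touch on impact concepts. This stands as far as it goes: the objective is not wholly without evidence. But the wording for the modified QOLRAD is also investigate, and that instrument receives four correlation pairings and a known-groups display. The weaker verb does not explain the omission.

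Second, the impact items are recorded through Part 2, with modified QOLRAD and MOS Sleep at visits 4 and 5 and SF-36v2 acute at visit 5. The SAP could contain validity analyses on those data. This stands as a limit on the conclusion. A reader might infer that the trial can never answer the objective, and the protocol does not support that. It supports only that the Part 1 construct-validity analyses, where the protocol places this work, omit the instrument.

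Third, a reader might extend the point to the modified RDQ, because 4.2 names GSRS, SF-36v2 acute, modified QOLRAD and OTE as its references while 6.3.6.1 has only "Modified RDQ vs GSRS: GSRS dimension scores will be based on responses at visit 2". From this one might conclude that 4.2 is not carried out, or that the modified RDQ rests on a single overlapping comparator. The text supports neither. The list in 4.2 is joint over validity, reliability, responsiveness and clinically meaningful change, and the subsections divide the roles. For the modified RDQ, GSRS serves construct validity (4.2.3), SF-36v2 acute serves meaningful change and the responder definition (4.2.4), and QOLRAD dimensions serve meaningful change (4.2.5). OTE serves responsiveness, meaningful change and the selection of stable patients (4.2.9). Section 6.3.6.1 follows that division. The GSRS has five dimensions, of which only the reflux dimension overlaps closely with the RDQ. Section 6.3.1 also relates an RDQ score to three QOLRAD dimensions, though to choose the weekly score.

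**Conclusion.** The point holds for the impact e-diary. One of seven validation objectives has no convergent, discriminant or known-groups analysis in the protocol: 0 of 5 pairings in 6.3.6.1 and no place in 6.3.6.2. What is planned is factor structure and description, which cannot show whether the diary items measure the same impact as the established scales.

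The conclusion rests on reading 6.3 as the full set of Part 1 analyses, which 6.1 supports by tying the SAP to Part 2 data. If the SAP does include construct-validity analyses of the impact items, the gap is in the protocol text and not in the trial as a whole.

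The omission does not affect safety or the other objectives, and no data are lost. It is worth correcting before the Part 1 results are examined, because expected patterns of correlation carry weight only if stated beforehand. Further comparisons of the modified RDQ with modified QOLRAD and SF-36v2 acute are optional and correct no error.

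**What to change.** 1. In 6.3.6.1, add Spearman correlations of the impact e-diary clusters with modified QOLRAD dimensions, MOS Sleep, SF-36v2 acute and GSRS at visit 2. Use the mean of the last seven registrations before visit 2 and the missing-data rule of 6.3.4.
2. State beforehand which pairs should correlate highly and which weakly. For example, diary sleep items should correlate highly with QOLRAD sleep disturbance and MOS Sleep, and diary clusters weakly with the GSRS diarrhoea and constipation dimensions. Give the expected sign: lower QOLRAD scores mean greater impact, and the diary sleep quality and depth items run opposite to the sleep disruption item.
3. Correlate the four sleep time and count items of 6.3.7.6 with MOS Sleep separately, since they lie outside the 11-point clusters.
4. Add the impact clusters to the GSRS known-groups display in 6.3.6.2.

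The cost is a few lines of protocol text and a few more tables and one more display. No new assessment or visit is needed, and there is no added burden on patients. The drawback is a larger number of correlations to read, which the stated expectations in item 2 keep in order.

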6.3.6.2 Known groups validity

The GSRS reflux syndrome dimension scores (see section 4.2.3) from visit 2 will be used to separate patients into three groups that can be expected to score differently in questions regarding heartburn and acid regurgitation in other instruments. The cut-off for the separation

will be based on previous data. The mean cluster score of the modified RDQ symptom clusters and modified QOLRAD clusters will be presented graphically by GSRS group.

For the modified RDQ, the derived symptom clusters of 24 h period values (see section 6.3.2) will be used. Symptom cluster scores will be defined as the mean or maximum (see section 6.3.1) daily symptom cluster intensity of the last 7 days prior to visit 2.

For the modified QOLRAD, the derived clusters (see section 6.3.3) will be used, using responses at visit 2.

Missing values

If a patient answered less than 50% of the items in a cluster, the cluster score will be set to missing.

6.3.7 Symptom pattern

6.3.7.1 Modified RDQ e-diary

For the modified RDQ items and derived symptom clusters (see section 6.3.2), the following variables will be presented with descriptive statistics:

- Number of days with symptoms during the last seven days prior to visit 2
- Mean symptom intensity during last seven days prior to visit 2
- Number of morning registrations with symptoms during the last seven mornings prior to visit 2
- Mean symptom intensity during the last seven morning registrations prior to visit 2

Frequency tables will be produced for

- Number of days with symptoms reported at visit 1 (one week recall)
- Symptom intensity reported at visit 1 (one week recall)

6.3.7.2 Modified QOLRAD

Mean and SD of cluster scores at visit 1 and visit 2 will be presented.

6.3.7.3 GSRS

Mean and SD of item and dimension scores at visit 1 and visit 2 will be presented.

6.3.7.4 Most troublesome symptoms

The frequency of the “most troublesome” and the “second most troublesome” symptom reported at visit 1 and visit 2 will be presented.

6.3.7.5 HADS

Frequency and proportion of patients with dimension scores 0-7 (normal), 8-10 (mild), 11-14 (moderate), 15-21 (severe) will be presented for the anxiety and depression dimension respectively.

6.3.7.6 Impact of symptoms e-diary items

For the items with responses on an 11 point NRS and the derived clusters (see section 6.3.4), the mean value will be presented graphically by day for the last seven days prior to visit 2. A cluster score will be calculated as the mean value of the item responses in the cluster.

Descriptive statistics will be calculated for the morning report items

- How long did it take you to fall asleep last night?
- How many times did you wake up after falling asleep?
- After falling asleep for the first time, how much total time did you spend awake during the night?
- How long did you sleep last night?

6.3.8 Demographic data and disease history

The following will be presented descriptively:

- Demographic variables (age, sex, race, BMI, nicotine use)
- History of GI symptoms
- History of PPI treatment
- IBS, Rome II and III criteria
- History of paresthesiae
- Medical and surgical history

6.4 Description of analysis sets, Part 2

The analysis sets for Part 2 analyses will be described in the SAP.

6.5 Methods of statistical analysis, Part 2

6.5.1 Test retest, modified RDQ

Test-retest reliability will be investigated for the modified RDQ using Intraclass Correlation Coefficients (ICC), using subjects in a stable condition between visit 2 and 4 (see section 6.3.5.1 for definition of ICC and stable condition). The test-retest reliability intraclass

correlation coefficient (R) and a 95% confidence interval will be estimated for each derived symptom cluster of 24 h period values (see section 6.3.2). Symptom cluster scores will be defined as the mean or maximum (see section 6.3.1) daily symptom cluster intensity of the 7 days prior to visit 2 and visit 4.

In order to be included in the test-retest calculations, a patient has to have non-missing symptom cluster scores at both visit 2 and visit 4.

6.5.2 Ability to detect change

6.5.2.1 Effect size calculations

The responsiveness of the different PRO questionnaires will be analysed by calculating the effect size. Effect sizes will be determined by OTE classifications at visit 5. The classifications will be presented in the SAP.

6.5.3 Clinically meaningful change (CMC)

Anchor based approach

Patients will be classified into sub groups based on their response to the OTE assessment at the visit after the 4 weeks treatment period. The following potential definitions of a clinically meaningful change will be derived and evaluated:

- An inpatient change from the last 7 days before first dose to the last 7 days of treatment with respect to the number of days with symptoms, below the median change observed in the subgroup of patients classified as “Moderately better” by the OTE.
- An inpatient change from the last 7 days before first dose to the last 7 days of treatment with respect to the number of days with symptoms, below the 25th quantile and the 10th quantile of the change observed in the subgroup of patients classified as “Unchanged” by the OTE.

Further details and additional potential anchor based definitions of clinically meaningful change will be given in the SAP.

The cumulative proportion of patients by the change in the number of days with symptoms, as defined above, will be presented by OTE classification.

Distribution based approach

The following potential definitions of a clinically meaningful change will be derived and evaluated:

- Having number of days with symptoms during the last 7 days of treatment less than the 10th quantile and the 5th quantile of the number of days with symptoms during the last 7 days before first dose.

Further details and additional potential distribution based definitions of clinically meaningful change will be given in the SAP.

Details on how to handle missing data will be given in the SAP.

